### **3. STUDY DESIGN**

#### **3.1 Study Description and Duration**

This three-month prospective, open-label, single-center, randomized investigator initiated clinical study seeks to investigate the efficacy of DEXTENZA when placed in the lower canaliculus (study eye) compared to topical corticosteroids (control eye) following bilateral SMILE surgery. In addition, the study will evaluate physician assessment of ease of DEXTENZA insertion

### **4. SELECTION, WITHDRAWAL, AND REPLACEMENT OF PATIENTS**

#### **4.1 Study Population**

The study aims to enroll 20 patients undergoing bilateral SMILE.

##### **4.1.1 Inclusion Criteria**

A patient's study eye must meet the following criteria to be eligible for inclusion in the study:

- Age 18 years and older
- Scheduled for bilateral SMILE surgery
- Willing and able to comply with clinic visits and study related procedures
- Willing and able to sign the informed consent form

##### **4.1.2 Exclusion Criteria**

A patient who meets any of the following criteria will be excluded from the study:

- Patients under the age of 18.
- Pregnancy (must be ruled out in women of child-bearing age with pregnancy test)
- Active infectious systemic disease
- Active infectious ocular or extraocular disease
- Obstructed nasolacrimal duct in the study eye(s)
- Hypersensitivity to dexamethasone
- Patients being treated with immunomodulating agents in the study eye(s)
- Patients being treated with immunosuppressants and/or oral steroids  
Patients with severe disease that warrants critical attention, deemed unsafe for the study by the investigator

#### **4.2 Treatment Logistics and Accountability**

##### **4.2.1 Packaging, Labeling, and Storage**

Intracanalicular dexamethasone insert must be stored in a secure area accessible only to the Investigator and their designee(s) and refrigerated and stored between 2° C and 8° C. Intracanalicular dexamethasone insert contains 0.4 mg dexamethasone and is designed to provide a sustained and tapered

release of therapeutic levels of dexamethasone to the ocular surface for up to 30 days for the reduction of post-surgical inflammation and pain associated with ocular surgery. Dexamethasone is an anti-inflammatory 9-fluoro-glucocorticoid (also termed a glucocorticoid agonist) and is the active ingredient found in MAXIDEX® 0.1% (dexamethasone ophthalmic suspension), which contains approximately 50 µg of dexamethasone per drop.

Study inserts will be supplied by Ocular Therapeutix in a sealed foil pouch containing one intracanalicular dexamethasone insert in a foam carrier.

Study inserts will be shipped to the site via overnight shipping using cold packs to maintain a temperature of 2° to 8° C. The Investigator, or an approved representative (e.g. pharmacist), will ensure that all study drug inserts are stored in a secured area, under recommended storage conditions and in accordance with applicable regulatory requirements. The shipping box is to be opened and stored immediately at the site in a refrigerator intended for investigational products at a temperature of 2° to 8°C.

When the insert is removed from the refrigerator, it should be visually inspected. Exposure of the insert to temperatures outside these limits is not recommended. Records of actual storage conditions (i.e. temperature log) at the study site must be maintained; and must include a record of the dates, when the refrigerator was checked, the initials of person checking, and the temperature.

#### **4.2.2 Supply and Disposition of Treatments**

Study insert will be shipped at a temperature of 2° to 8°C to the investigator as needed during the study.

#### **4.2.3 Treatment Accountability**

All study insert accountability records will be kept current.

The investigator will account for all opened and unopened packaging of study inserts. These records will contain the dates, quantity, and study medication

- Inserted in each patient,
- disposed of at the site or returned to Ocular Therapeutix

All accountability records will be made available for inspection by regulatory agency inspectors.

### **4.3 Concomitant Medications and Procedures**

At the discretion of their physician, patients may continue to receive all medications and standard treatments administered for other conditions.

**5. STUDY SCHEDULE OF EVENTS AND VISIT DESCRIPTIONS**

**5.1 Schedule of Events**

Study assessments and procedures are presented by visit in [Table 1](#).

**[name] STUDY**

**Table 1 Schedule of Events**

Study Procedure	Screening/ Baseline	Surgical Visit Day 0	Day 1	Day 7	Day 30	3 MTH post-op	Early Termin- ation
Visit	VISIT 1	VISIT 2	VISIT 3	VISIT 4	VISIT 5	VISIT 6	
Windows for Visits	(Day -30 to -1)			+/- 3 day	+/- 5 days	+/- 7 days	
Inclusion/Exclusion	x						
Informed Consent	x						
Demographics	x						
Medical History and Concurrent Illnesses	x						
Concomitant Medications	x	x	x	x	x	x	
Distance UCVA testing	x		x	x	x	x	
BCVA (ETDRS at 4m)	x			x	x	x	
Ophthalmic Examination (w or w/o dilated fundus exam)	x	x	x	x	x	x	
Pentacam	x						
Intraocular Pressure	x			x	x	x	
Indicate the incision type, location, and size (mm)			x	x	x	x	
Record any surgical complications	x	x	x	x	x	x	
Subject reported AEs prior to or after surgery	x	x	x	x	x	x	
Intracanalicular dexamethasone insert*		x					
Patient Treatment Preference			x	x	x	x	
Ocular Pain Assessment	x		x	x	x	x	
Anterior chamber cell count	x		x	x	x	x	
Anterior chamber cell flare	x		x	x	x	x	
Insert Visualization		x	x	x	x	x	

## **5.2 Study Visit Descriptions**

### **5.2.1 Study Procedures**

#### **Screening/Baseline**

- Inclusion/Exclusion Criteria
- Informed consent
- Demographics
- Medical history and concurrent illnesses
- Concomitant medications
- Ocular Pain Assessment Scale
- Distance UCVA (OD, OS, OU)
- Best-corrected visual acuity as measured by ETDRS chart at 4m
- Intraocular Pressure
- Ophthalmic Examination (including dilated fundus exam)
  - anterior chamber cell count
  - anterior chamber cell flare
- Pentacam
- IOP
- Subject reported AE's prior to or after surgery

#### **Visit 2 (Surgery Day)**

- Concomitant medications
- Ophthalmic exam
- Intracanalicular dexamethasone insert
- Insert visualization
- Record any surgical complications
- Subject reported AE's prior to or after surgery
- Physician ease of use

#### **Visit 3 (Day 1 post op)**

- Concomitant medications
- Ophthalmic exam
- Distance UCVA (OD, OS, OU)
- Record any surgical complications
- Indicate the incision type, location and size (mm)
- Subject reported AEs after surgery
- Patient Treatment Assessment
- Ocular Pain assessment
- Ocular inflammation assessment
- Insert visualization

#### **Visit 4-6 (1 week- 3months after surgery)**

- Concomitant medications
- Ophthalmic exam
- Distance UCVA (OD, OS, OU)
- BCVA (ETDRS at 4m) at Visit 4,5,6 (OD, OS, OU)
- IOP at Visit 4,5,6
- Record any surgical complications
- Indicate the incision type, location and size (mm)
- Subject reported AEs after surgery
- Patient Symptoms Questionnaire
- Ocular Pain Assessment Scale
- Ocular inflammation assessment
- Insert visualization

### **5.2.2 Unscheduled Visits**

All attempts should be made to keep patients on the study schedule. Unscheduled visits may be necessary to repeat testing following abnormal laboratory results, for follow-up of AEs, or for any other reason, as warranted.

### **5.2.3 Adverse Event Information Collection**

The investigator (or designee) will record all AEs that occur during the study. The definition of an AE and SAE, and information on the determination of severity and relationship to treatment are provided in [Section 7](#).

## **5.3 Rescue Criteria**

- Patients should be rescued at any time at the discretion of the investigator.
- The following rescue criteria are to be applied by the investigator on post operative visit 1 or later:
  - $\geq$  Grade 2+ anterior chamber cells
  - $\geq$  Grade 3+ anterior chamber flare
  - $\geq$  Grade 4+ pain

## **6. SAFETY DEFINITIONS, REPORTING, AND MONITORING**

### **6.1 Definitions**

#### **6.1.1 Adverse Event**

An AE is any untoward medical occurrence in a patient administered a study drug which may or may not have a causal relationship with the study drug. Therefore, an AE is any unfavorable and unintended sign (including abnormal laboratory finding), symptom, or disease which is temporally associated with the use of a study drug, whether or not considered related to the study drug.

An AE also includes any worsening (i.e. any clinically significant change in frequency and/or intensity) of a pre-existing condition that is temporally associated with the use of the study drug.

### 6.1.2 Serious Adverse Event

A SAE is any untoward medical occurrence that at any dose:

- Results in **death** – includes all deaths, even those that appear to be completely unrelated to study drug (e.g. a car accident in which a patient is a passenger).
- Is **life-threatening** – in the view of the investigator, the patient is at immediate risk of death at the time of the event. This does not include an AE that had it occurred in a more severe form, might have caused death.
- Requires in-patient **hospitalization** or prolongation of existing hospitalization. In-patient hospitalization is defined as admission to a hospital or an emergency room for longer than 24 hours. Prolongation of existing hospitalization is defined as a hospital stay that is longer than was originally anticipated for the event, or is prolonged due to the development of a new AE as determined by the investigator or treating physician.
- Results in persistent or significant **disability/incapacity** (substantial disruption of one's ability to conduct normal life functions).
- Is a **congenital anomaly/birth defect**
- Is an **important medical event** – Important medical events may not be immediately life-threatening or result in death or hospitalization, but may jeopardize the patient or may require intervention to prevent 1 of the other serious outcomes listed above (e.g., intensive treatment in an emergency room or at home for allergic bronchospasm; blood dyscrasias or convulsions that do not result in hospitalization; or development of drug dependency or drug abuse). Any malignancy (other than basal cell skin cancers) would be considered a medically important event.

### 6.2 Recording and Reporting Adverse Events

All AEs and SAEs will be recorded only if they are medically relevant.

All SAEs, regardless of assessment of causal relationship to study insert will be reported to Ocular Therapeutix.

To report an SAE, Ocular Therapeutix will be contacted at the following:

[[contact]](mailto:[contact])

SAE [contact]

The investigator will promptly report to the IRB all unanticipated problems involving risks to patients. This includes death from any cause and all SAEs

related to the use of the study insert. All SAEs will be reported to the IRB, regardless of assessed causality.

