## **7. STUDY VARIABLES**

### **7.1 Demographic and Baseline Characteristics**

Baseline characteristics will include standard demography (e.g. age, race, weight, height, etc.), disease characteristics including medical history, and medication history for each patient.

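### Section 6.2 limits adverse event recording to events judged medically relevant, an undefined filter that conflicts with the rule in Section 5.2.3 to record every adverse event

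*Protocol*

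**What the plan says.** Protocol Section 5.2.3 sets an unfiltered rule: "The investigator (or designee) will record all AEs that occur during the study". Section 6.2 opens with a filtered one: "All AEs and SAEs will be recorded only if they are medically relevant".

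The surrounding text bears on how these can be read:

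- Section 6.1.1 defines the events in scope: "An AE is any untoward medical occurrence in a patient administered a study drug which may or may not have a causal relationship". It sets no general relevance threshold.
- Section 6.1.2, on death as a seriousness criterion, "includes all deaths, even those that appear to be completely unrelated to study drug".
- Section 6.2 goes on to require that "All SAEs, regardless of assessment of causal relationship to study insert will be reported to Ocular Therapeutix", and that "All SAEs will be reported to the IRB, regardless of assessed causality".
- Section 5.2.3 says that the AE and SAE definitions and "information on the determination of severity and relationship to treatment are provided in" Section 7. Section 7 has one subsection, 7.1, which begins "Baseline characteristics will include standard demography" and covers only demographic and baseline variables.

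The SAP does not mention adverse events.

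**The concern.** Both sentences govern the same act, recording, for the same events. One admits every AE; the other admits only those that pass a test the protocol does not describe. If Section 6.2 is the rule followed, non-serious events that no scheduled measurement picks up may never enter the record.

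The design makes this matter more. Section 3.1 describes an open-label study in which each patient has an insert eye and a drop eye. An undefined judgement made with treatment known could drop events unequally between the two eyes. That is an inference from the design; nothing in the documents shows that it happened. Even without such an imbalance, any AE count reported later could not be interpreted unless the reader knew which rule produced it.

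**Working it through.** No arithmetic applies beyond simple counts, so the check sets the rules side by side.

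**Step 1. What each rule requires, by type of event.**

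| Event | Section 5.2.3 | Section 6.2, opening sentence | Result |
|---|---|---|---|
| AE judged relevant | Record | Record | Agree |
| Non-serious AE judged not relevant | Record | Do not record | Conflict |
| SAE judged not relevant | Record | Do not record | Conflict on recording, but later sentences of 6.2 still require reporting to the supplier and the IRB |

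The rules agree throughout only if the second and third rows are empty, that is, if every AE counts as relevant. The restriction in Section 6.2 would then exclude nothing.

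**Step 2. Whether the protocol defines the filter.** The term occurs 1 time, in Section 6.2, with 0 definitions. The closest wording is the important medical event criterion in Section 6.1.2. That separates serious from non-serious events and cannot say which non-serious events are relevant. Section 6.1.1 asks for clinical significance only when a pre-existing condition worsens, so it sets no threshold for new events.

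**Step 3. Whether the cross-reference helps.** Section 5.2.3 sends the reader to Section 7. The definitions are in Section 6, Section 7 holds baseline variables only, and no criteria for severity or relationship to treatment appear in the documents. The pointer does not settle the conflict.

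**Step 4. Whether the visit schedule settles it.** Table 1 marks the subject-reported AE row at all 6 scheduled visits (screening, Day 0, Day 1, Day 7, Day 30, 3 months), and each of the four visit lists in Section 5.2.1 has a matching line. Events are therefore asked about throughout. Asking does not determine which answers are written down.

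**Step 5. What is captured regardless.** Pain, anterior chamber cell and flare, visual acuity, intraocular pressure and surgical complications have their own rows in Table 1. The gap is therefore mainly non-serious events outside those rows.

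**Step 6. What rests on the AE record.** AEs are not among the primary or secondary measures in the synopsis or in Sections 2.1 and 2.2, and the SAP plans no AE analysis. No planned endpoint or test changes.

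**The case against.** The strongest reply is that the two rules can be harmonised. Section 6.1.1 already confines AEs to medical occurrences and asks for a clinically significant change when a pre-existing condition worsens, so Section 6.2 could be a loose restatement of the definition. On that view the drafting is ambiguous but not contradictory. This reading is possible, but it leaves the restriction in Section 6.2 with no function, and the clinical significance wording covers only pre-existing conditions.

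Second, Section 5.2.3 names the investigator or designee as recorder, and with a single center there can be no divergence between sites. Both points are fair. They identify who records, but not the standard to be applied, and one center can still apply an undefined standard unevenly over time or between eyes.

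Third, there are further safety nets. An ophthalmic examination and concomitant medications are scheduled at all six visits, patient call-backs per eye are a secondary measure, and Sections 6.2 and 8.4 require unanticipated problems and safety-relevant events to go to the IRB. These do narrow the exposure to mostly low-consequence events, but none of them replaces an AE record.

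Fourth, the SAE strand is mainly one of wording, since every SAE must be reported whatever the recording sentence says. Section 6.2 also narrows capture relative to the AE definition without contradicting it, because a definition imposes no duty to record. Both points stand. The finding rests on Section 5.2.3 against Section 6.2, chiefly for non-serious events.

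**Conclusion.** The concern holds. Sections 5.2.3 and 6.2 conflict for every AE not judged medically relevant, and nothing in the protocol or SAP resolves the conflict. Section 6.2 as written permits incomplete safety capture at the discretion of an unblinded investigator; this is a defect in a stated rule, not merely missing detail.

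The size cannot be computed, because there is no AE rate and no definition of the filter. In kind, the harm is limited to non-serious events without their own row in Table 1. No planned endpoint or analysis is affected. The possibility of unequal omission between eyes rests on the open-label design and is not demonstrated. How the filter was applied in practice is unknown.

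The conflict should be corrected because the rule concerns safety and the correction costs almost nothing. The faulty cross-reference is a separate, editorial point.

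**What to change.** Delete the relevance qualifier from the opening sentence of Section 6.2 so that it agrees with Section 5.2.3. Any classification by relevance should follow recording and not decide it. Defining the term and amending Section 5.2.3 to match would also remove the contradiction, but it would keep a filter on safety data; deletion is simpler and gives fuller capture.

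At the same time, correct the cross-reference in Section 5.2.3 from Section 7 to Section 6, and either supply the severity and relationship criteria it promises or remove that promise.

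The cost is one deleted qualifier, one corrected reference and any criteria added, with IRB approval before implementation as Section 8.4 requires. No visit is added, because AEs are already asked about at all 6 scheduled visits.

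The SAP is dated 22 November 2022 and written in the past tense, which suggests that conduct is finished. If so, an amendment cannot recover unrecorded events. The study report should then state which recording rule was followed and disclose any filtering, at the cost of one statement.

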## **7. STUDY VARIABLES**

### **7.1 Demographic and Baseline Characteristics**

Baseline characteristics will include standard demography (e.g. age, race, weight, height, etc.), disease characteristics including medical history, and medication history for each patient.

## **8. ETHICAL AND REGULATORY CONSIDERATIONS**

### **8.1 Good Clinical Practice Statement**

It is the responsibility of the investigator(s) to ensure that this clinical study will be conducted in accordance with the ethical principles that have their origin in the Declaration of Helsinki, and that are consistent with the ICH guidelines for Good Clinical Practice (GCP) and applicable regulatory requirements.

### **8.2 Informed Consent**

The principles of informed consent are described in ICH Guidelines for GCP.

Ocular Therapeutix will have the right to review and comment on the informed consent form.

It is the responsibility of the investigator or designee (if acceptable by local regulations) to obtain written informed consent from each patient prior to his/her participation in the study and after the aims, methods, objectives, and potential hazards of the study have been explained to the patient in language that he/she can understand. The ICF will be signed and dated by the patient and by the investigator or authorized designee who reviewed the ICF with the patient.

The original ICF will be retained by the investigator as part of the patient's study record, and a copy of the signed ICF will be given to the patient.

If new safety information results in significant changes in the risk/benefit assessment, the ICF will be reviewed and updated appropriately. All study patients will be informed of the new information and provide their written consent if they wish to continue in the study. The original signed revised ICF will be maintained in the patient's study record and a copy will be given to the patient.

### **8.3 Patient Confidentiality and Data Protection**

The investigator will take all appropriate measures to ensure that the anonymity of each study patient will be maintained.

The patient's and investigator's personal data will be treated in compliance with all applicable laws and regulations.

#### **8.4 Institutional Review Board**

An appropriately constituted IRB, as described in ICH Guidelines for GCP, will review and approve:

- The protocol, ICF, and any other materials to be provided to the patients (e.g. advertising) before any patient may be enrolled in the study
- Any amendment or modification to the study protocol or ICF before implementation, unless the change is necessary to eliminate an immediate hazard to the patients, in which case the IRB will be informed as soon as possible

Ongoing studies will be reviewed by the IRB/EC on an annual basis or at intervals appropriate to the degree of risk.

In addition, the IRB will be informed of any event likely to affect the safety of patients or the continued conduct of the clinical study.

A copy of the IRB approval letter will be sent to Ocular Therapeutix prior to shipment of drug insert supplies to the investigator. The approval letter will include the study title, the documents reviewed, and the date of the review.

Records of the IRB review and approval of all study documents (including approval of ongoing studies) will be kept on file by the investigator.

REFERENCES

1. DEXTENZA (dexamethasone insert) Prescribing Information, Ocular Therapeutix, Inc. 2019 <http://www.dextenza.com/wp-content/uploads/2019/06/NDA-208742-S001-Dextenza-labeling-19Jun19.pdf>
3. Walters TR, et al. Efficacy and Safety of Sustained Release Dexamethasone for the Treatment of Ocular Pain and Inflammation after Cataract Surgery: Results from Two Phase 3 Studies. *J Clin Exp Ophthalmol.* 2016; 7(4): 572.

Prospective, Randomized, Fellow Eye-Controlled Study of Postoperative Pain and Inflammation Control with an Intracanalicular Dexamethasone 0.4 mg Ophthalmic Insert Following Small Incision Lenticule Extraction

22NOVEMBER2022

NCT04380857

Statistical Analysis Plan:

No formal power analysis was conducted, and the sample size was set at 40 eyes based on the sample size used in several similar prior studies.^{18–20} Chi-square tests were used to compare proportions and t-tests to compare means. The level of significance was set at 0.05.

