### CLINICAL STUDY PROTOCOL SYNOPSIS

TITLE	A randomized controlled clinical trial assessing the efficacy of DEXTENZA, sustained release dexamethasone 0.4 mg insert, when placed within the lower eye eyelid canaliculus in comparison to topical prednisolone acetate following bilateral small incision lenticule extraction (SMILE).
SITE LOCATION(S)	Toledo LASIK & Cataract
PRINCIPAL INVESTIGATOR	[name]
OBJECTIVE(S)	Assessing DEXTENZA efficacy when placed within the lower eyelid canaliculus post SMILE in comparison to topical prednisolone acetate.
STUDY DESIGN	A randomized controlled clinical trial assessing the efficacy of DEXTENZA, sustained release dexamethasone 0.4 mg insert, when placed within the lower eye eyelid canaliculus in comparison to topical prednisolone acetate following bilateral small incision lenticule extraction (SMILE).
STUDY DURATION	3 months
ESTIMATED STUDY COMPLETION DATE	3 months
POPULATION	
Sample Size:	20
Target Population:	Patients undergoing bilateral SMILE
TREATMENT(S)	
Study Drug	Sustained Release Dexamethasone, 0.4 mg
Dose/Route/Schedule:	All patients will receive: First eye randomized for either topical prednisolone acetate (Control eye) or lower eyelid canaliculus DEXTENZA insertion (Study Eye) insertion and the contralateral eye receiving the opposite treatment in the OR following SMILE
ENDPOINT(S)	

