**Primary:**

- Patient preference as measured by Patient Symptoms Questionnaire
- Mean change in pain score
  - Post op pain scores as measured on a scale from 0-10 (Days 1,7,30)
- Mean change in AC cell and flare score
  - Post op inflammation scores as measured on a scale of 0-4 (Days 1,7,30)
    - Absence of cell to be defined as a grade of: 0-0.5
    - Absence of flare to be defined as a grade of: 0-1

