**Secondary:**

- Mean change BCVA
- Mean change in UCVA
- Proportion of patient call backs on post-operative management per eye (E.H.R. chart documentation)

---

TABLE OF CONTENTS

Clinical Study Protocol Synopsis.....	2
List of Tables.....	5
1. Introduction and Rationale.....	6
1.1    Introduction .....	6
1.2    Rationale .....	6
1.2.1    Rationale for Study Design .....	6
2. Study Objectives.....	6
2.1    Primary Objective.....	6
2.2    Secondary Objectives .....	6
3. Study Design.....	7
3.1    Study Description and Duration .....	7
4. Selection, Withdrawal, and Replacement of Patients .....	7
4.1    Study Population .....	7
4.1.1    Inclusion Criteria.....	7
4.1.2    Exclusion Criteria.....	7
4.2    Treatment Logistics and Accountability.....	7
4.2.1    Packaging, Labeling, and Storage.....	7
4.2.2    Supply and Disposition of Treatments .....	8
4.2.3    Treatment Accountability.....	8
4.3    Concomitant Medications and Procedures .....	8
5. Study Schedule of Events and Visit Descriptions.....	9
5.1    Schedule of Events .....	9
5.2    Study Visit Descriptions.....	11
5.2.1    Study Procedures .....	11
5.2.2    Unscheduled Visits .....	12
5.2.3    Adverse Event Information Collection .....	12
5.3    Rescue Criteria .....	12
6. Safety Definitions, Reporting, and Monitoring .....	12
6.1    Definitions .....	12
6.1.1    Adverse Event.....	12
6.1.2    Serious Adverse Event .....	13

6.2	Recording and Reporting Adverse Events.....	13
7.	Study Variables .....	14
7.1	Demographic and Baseline Characteristics .....	14
8.	Ethical and Regulatory Considerations.....	14
8.1	Good Clinical Practice Statement.....	14
8.2	Informed Consent .....	14
8.3	Patient Confidentiality and Data Protection .....	14
8.4	Institutional Review Board.....	15
LIST OF TABLES		
Table 1	Schedule of Events.....	10

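### The trial compares two eyes of the same patient, but the SAP names only unqualified chi-square tests and t-tests on 40 eyes and specifies no paired method.

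*SAP*

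**What the plan says.** The design is within-patient. The SAP title calls it a "Prospective, Randomized, Fellow Eye-Controlled Study". In the protocol synopsis (Dose/Route/Schedule) the first eye is randomized to insert or drops, with "the contralateral eye receiving the opposite treatment in the OR following SMILE". Protocol section 4.1 states: "The study aims to enroll 20 patients undergoing bilateral SMILE".

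The SAP counts eyes: "the sample size was set at 40 eyes based on the sample size used in several similar prior studies". It states that no formal power analysis was done and sets significance at 0.05. Its only sentence on methods is "Chi-square tests were used to compare proportions and t-tests to compare means". The protocol has no statistics section. Neither document mentions a paired t-test, McNemar's test, a mixed model or any other handling of correlation between fellow eyes.

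The per-eye means in the synopsis are change in pain, anterior chamber cell and flare (primary), and BCVA and UCVA (secondary). The one listed per-eye proportion is secondary: "Proportion of patient call backs on post-operative management per eye (E.H.R. chart documentation". The primary list also defines cut-offs for absence, for example "Absence of cell to be defined as a grade of: 0-0.5", although the listed endpoint is the mean change in score. Patient preference is also primary, and Table 1 collects it at Day 1, Day 7, Day 30 and 3 months.

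**The concern.** Two eyes of one person share surgeon, patient, healing response and pain reporting, so their outcomes may well move together. A fellow-eye design is meant to exploit this, because the within-patient difference removes what the eyes share. A test that treats the 40 eyes as 20 versus 20 independent observations discards that gain and attaches the wrong standard error to the treatment difference.

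For means, the stake is a missed difference, or an interval too wide to interpret, in a study of only 20 pairs with no power calculation. A non-significant comparison with active drops could be misread as similarity. For per-eye proportions, Pearson's p-value is the same whichever eyes belong to the same patient, so it does not use the structure that the design created.

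**Working it through.** **Count.** 20 patients × 2 eyes = 40 eyes, which reproduces the SAP's figure. The documents give no effect size, SD, event rate or power, so there is nothing further to reproduce.

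**Assumptions.** 20 complete pairs; two-sided 0.05 (the SAP does not state sidedness); equal SD in both eyes; correlation rho between the two eyes' values from 0 to 0.8. The documents give no rho.

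**Means.** With single-eye SD = 1, the true standard error of the difference is sqrt(2(1−rho)/20). A two-sample test estimates it as sqrt(2/20), too large by the factor 1/sqrt(1−rho): 1.05 at rho 0.1 and 1.41 at rho 0.5. The 95% half-widths, at the true SD, are:
- two-sample (38 df): 2.024 × sqrt(2/20) = 0.64 SD at any rho;
- paired (19 df), rho 0.5: 2.093 × sqrt(2 × 0.5/20) = 0.47 SD.

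Type I error and two-sample power come from 200,000 simulated trials per setting. Paired power is from the noncentral t, and simulation agrees to within about one point.

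| rho | Two-sample type I error | Power at 0.5 SD, two-sample | Power at 0.5 SD, paired | Half-width, two-sample | Half-width, paired |
|---|---|---|---|---|---|
| 0 | 5.0% | 34% | 32% | 0.64 | 0.66 |
| 0.1 | 3.9% | 33% | 35% | 0.64 | 0.63 |
| 0.3 | 2.1% | 31% | 43% | 0.64 | 0.55 |
| 0.5 | 0.7% | 29% | 56% | 0.64 | 0.47 |
| 0.8 | 0.01% | 22% | 92% | 0.64 | 0.30 |

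The paired test holds about 5% type I error at every rho.

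**Proportions.** Assume each eye is scored yes or no for a call-back, with the same true rate of 10% to 50% in both arms and latent-normal correlation between eyes. Pearson's type I error is about 3.9% to 5.3% at latent rho 0, and 1.4% to 2.1% at latent rho 0.5. At latent rho 0.5, exact McNemar gives 0.1% to 1.5% and mid-p McNemar 0.6% to 3.5%. Power at latent rho 0.5 is:

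| True rates | Pearson | Exact McNemar | Mid-p McNemar |
|---|---|---|---|
| 30% v 10% | 33% | 20% | 33% |
| 50% v 20% | 53% | 47% | 60% |
| 40% v 10% | 64% | 52% | 66% |
| 20% v 5% | 26% | 8% | 18% |

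**Illustrative counts.** These are not trial data. Phi is the within-patient association.

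For 8 v 2 of 20 eyes, Pearson chi-square = 0.3² / (2 × 0.25 × 0.75/20) = 4.8, p = 0.028 however the eyes pair. For 12 v 6, it is 0.3² / (2 × 0.45 × 0.55/20) = 3.64, p = 0.057.

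| Totals | Patients positive in both eyes | Discordant pairs | Phi | McNemar mid-p |
|---|---|---|---|---|
| 8 v 2 | 0 | 8 v 2 | −0.27 | 0.065 |
| 8 v 2 | 1 | 7 v 1 | 0.07 | 0.039 |
| 8 v 2 | 2 | 6 v 0 | 0.41 | 0.016 |
| 12 v 6 | 3 | 9 v 3 | −0.13 | 0.092 |
| 12 v 6 | 4 | 8 v 2 | 0.09 | 0.065 |
| 12 v 6 | 6 | 6 v 0 | 0.53 | 0.016 |

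In these tables, significance is lost under mid-p only with negative association (8 v 2, no patient positive in both eyes). It can be gained with positive association (12 v 6, six such patients).

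**The case against.** The strongest reply is that this may be only a reporting gap. A study titled as fellow-eye-controlled may well have used paired t-tests, and McNemar's statistic is itself referred to a chi-square distribution. That stands as a limit: the documents do not show that independent-samples tests were run, and a reader who infers so goes beyond them. But the title describes the design, not the degrees of freedom of the test, and an unqualified chi-square comparison of proportions is normally read as Pearson's.

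Second, the proportion half is narrow. Call-backs are the only listed per-eye proportion, and the wording could mean the share of calls about each eye rather than the share of eyes with a call. In that case McNemar on 20 pairs would not directly apply. Absence of cell or flare enters only if it is compared as a proportion. All of this stands.

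Third, the error is conservative for positively correlated eyes, and the large power gaps need an assumed rho of 0.5 or more. This also stands. A reader might infer that significant results would be spurious, or that McNemar would recover power generally. Neither follows: false positives are not inflated under positive correlation, and exact McNemar has less power than Pearson in all four settings above. McNemar is recommended because it answers the paired question.

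**Conclusion.** The concern holds as a failure to specify paired analysis in a paired design. Read at face value, the SAP applies an independent-groups test to any per-eye proportion and leaves open whether the t-tests discard the pairing.

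For means, the harm is conditional on two-sample tests and positive correlation. It ranges from almost nothing at rho 0 to 0.1, to roughly half the power at an assumed rho of 0.5, with an interval about 37% wider (0.64/0.47 = 1.37). For call-backs scored yes/no, Pearson's test ignores the pairing and is conservative under positive correlation. The case for change there is fit to the design rather than power.

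Patient preference does not share this defect: it gives one answer per patient at a given visit, and a one-sample test is compatible with the SAP's wording. However, it is collected at four visits and the SAP does not say which is tested. The point should be fixed; it does not show that any reported result is wrong.

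**What to change.** - State the unit of analysis as the patient: 20 pairs (40 eyes).
- For pain, cell, flare, BCVA and UCVA, name a paired t-test on the within-patient insert-minus-drop difference.
- Define the call-back outcome. If it is yes/no per eye, use McNemar's test (mid-p, or exact with its conservatism at 20 pairs noted), and do the same for absence of cell or flare if compared as proportions.
- Report each paired difference with its 95% confidence interval.
- Test preference on one answer per patient at a stated visit, by exact binomial or one-sample chi-square.
- Because the SAP describes its tests in the past tense, state which were run and re-run any that were unpaired.

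The cost is SAP wording and, if needed, a small re-analysis of existing data, with no new patients, visits or measurements. The statistical price for means is about 1 to 2 points of power if rho is near 0 (34% v 32% at 0.5 SD).
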